6-week check	Written questionnaire (Appendix 6) administered by telephone to GP to determine pregnancy outcome and medically attended adverse events in mother since last contact.	Written questionnaire (Appendix 6) administered by telephone to GP practice to capture birth history, weight and head circumference, any congenital abnormalities, neonatal death (<29 days) Details of 6-week check and confirm receipt of 6-week vaccination. Document any prior GP or hospital visits.	If an unsolicited adverse event is noted during these calls, it will follow the same safety reporting procedures as other AEs in the study.
3–6 month check		Weight, head circumference, vaccination status, and standardised clinical examination by Plunket Nurse as recorded in Well Child book (Appendix 6). ³	
1-year follow-up		Final contact with mother about pertussis exposure and/or symptoms. Vaccination status – if not completed infant vaccinations by 6 months.	

1 Three attempts will be made to contact mother by telephone within 1 week of notification of receipt of Tdap. If an e-mail address is available this will also be used if telephone contact is unsuccessful.

2 Written questionnaire will be sent to mother before 4 weeks have elapsed since receipt of vaccine. Telephone contact will be made at 4 weeks of receipt of vaccine and two further times if the completed questionnaire has not been received within 1 week.

3 Mothers will be encouraged to attend Plunket for check ups during the first 6 months. If there is no available recorded weight and head circumference between 3-6 months of age this will be done by a member of the study team. The mother will be contacted three times via email or phone to get this information.

4 Three attempts will be made by phone or email to contact the mother each month

*Persistent cough lasting for >10 days and/or post-tussive vomiting

** Close contact defined as being in the same room as the person for > 1 hour or 5 minutes of face to face contact with a person with proven pertussis who was symptomatic.

Data management/Data confidentiality

Data will be managed and protected according to the requirements of the Ethical approval. An Access database will be developed to receive the data reported on the survey forms (Study Two and Three).

Data set fields will be identified

Code tables will be created

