3-6 month check		Weight, head circumference, vaccination status, and standardised clinical examination by Plunket Nurse as recorded in Well Child book (Appendix 6). ³	
1-year follow-up		Final contact with mother about pertussis exposure and/or symptoms. Vaccination status – if not completed infant vaccinations by 6 months.	

¹ Three attempts will be made to contact mother by telephone within 1 week of notification of receipt of Tdap. If an e-mail address is available this will also be used if telephone contact is unsuccessful.

² Written questionnaire will be sent to mother before 4 weeks have elapsed since receipt of vaccine. Telephone contact will be made at 4 weeks of receipt of vaccine and two further times if the completed questionnaire has not been received within 1 week.

³ mothers will be encouraged to attend Plunket for checkups during the first 6 months. If there is no available recorded weight and head circumference between 3-6 months of age this will be done by a member of the the study team. The mother will be contacted 3 times via email or phone to get this information.

⁴ Three attempts will be made by phone or email to contact the mother each month

*Persistent cough lasting for >10 days and/or post-tussive vomiting

** Close contact defined as being in the same room as the person for > 1 hour or 5 minutes of face to face contact with a person with proven pertussis who was symptomatic.

Study instruments

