Appendix 1: Consent form

Appendix 2: Information sheet for mother

Appendix 3: Structured questionnaire for GP practice – information on mother

Appendix 4: Telephone survey questionnaire (adverse events in mother)

Appendix 5: Written questionnaire (medically attended adverse events in mother in first 4 weeks after vaccine)

Appendix 6: Structured questionnaire for GP practice (Details of pregnancy outcomes, standardised clinical examination of baby at 6-week check)

Appendix 7: Information from clinical examination by Plunket Nurse between 3-6 months of age (outcomes for infant)

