Receipt of 3 month vaccination	Yes  No  Date:.....

Appendix 7: Information from clinical examination by Plunket Nurse between 3-6 months of age (outcomes for infant)

Study Title: Safety Monitoring of Adverse Reactions to Tdap Vaccine in Pregnancy

Information to be collected from Well Child book from any assessment from a Carer between the ages of **3 and 6 months**. i.e Plunket or GP

Date of assessment	
Age at assessment	
Weight in Kg	
Head circumference (cm)	
Length (cm)	
3 month vaccination (if missed on 6 week form)	Yes  No  Date:.....
5 month vaccination	Yes  No  Date:.....
Any concerns about developmental progress requiring medical referral	

* The Ministry of Health definition for age appropriate vaccination will be used, being receipt of the six-week immunisation within four weeks of due date and within six weeks of due date for the three-month, five-month and 15-month immunisations.

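### The Study Three 3–6 month form has no fields for the clinical examination its schedule promises, and no structured field for congenital abnormalities recognised after the 6-week check

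*Protocol*

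**What the plan says.** The Study Three schedule appears twice: in the main protocol (Study procedures, Study Three) and in the Canterbury protocol attached as Appendix 8 (Study assessments and procedures). In both, the infant column for the 3–6 month check lists two growth measurements (weight and head circumference), the infant's vaccination status, and a "standardised clinical examination by Plunket Nurse as recorded in Well Child book", followed by a reference to Appendix 6. The main protocol explains that appendix numbers in this table are those of the Canterbury protocol.

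The Canterbury list of study instruments describes Appendix 6 as "Structured questionnaire for GP practice (Details of pregnancy outcomes, standardised clinical examination of baby at 6-week check". The 3–6 month instrument is Appendix 7, whose title presents it as information from the Plunket Nurse's clinical examination. Its instruction reads "Information to be collected from Well Child book from any assessment from a Carer between the ages of" 3 and 6 months, with Plunket or GP given as examples. Its only clinical item besides measurements and vaccinations is "Any concerns about developmental progress requiring medical referral".

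The Canterbury primary objectives include describing the babies' outcomes. Birth history, weight, head circumference and congenital abnormalities are named, with no age limit. The main protocol's clinical hypothesis extends infant outcomes to one year of age.

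**The concern.** A schedule row and its data form should agree. If the row promises an examination and the form has nowhere to enter it, the examination may take place and be written in the Well Child book, yet never become study data. This is the only scheduled systematic clinical look at the infants after the 6-week check, so the gap falls on the later part of follow-up.

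At stake is how completely infant outcomes are described. Some abnormalities may not be recognised at birth or at 6 weeks. Without a structured prompt at 3–6 months, their capture depends on someone volunteering them. Incomplete capture can only lower the count. The Canterbury Statistical Analysis section compares AE and SAE rates with published background rates, and a congenital anomaly counts as an SAE. If those published rates include anomalies recognised later in infancy, the comparison would tilt towards reassurance. The protocol does not state the age window of those rates.

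**Working it through.** The plan gives no figure to reproduce. The check is a field-by-field comparison.

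**1. Items promised at 3–6 months against fields on the Canterbury Appendix 7**

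| Schedule item | Field on Appendix 7 |
|---|---|
| Weight | Yes |
| Head circumference | Yes |
| Vaccination status | Yes (3-month if missed earlier; 5-month) |
| Standardised clinical examination | None, apart from the developmental-concern item |

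The remaining fields are date of assessment, age and length. Three of the four promised items have a field.

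**2. The same content on the 6-week form (Canterbury Appendix 6)**

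| Content | 6-week form | 3–6 month form |
|---|---|---|
| Eye, heart, lung, neurological, hip or musculoskeletal findings (yes/no) | 5 items | 0 |
| Congenital abnormalities (yes/no, details) | 1 item, plus 1 on the pregnancy-outcome page | 0 |

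**3. Does the citation of Appendix 6 close the gap?** No. Appendix 6 is completed with the GP practice for birth and the 6-week check. Its clinical page is headed for 6 weeks and has no 5-month vaccination item. Neither form, used as printed, delivers the whole 3–6 month row.

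**4. Source of the data.** The schedule names the Plunket Nurse; Appendix 7 accepts an assessment by any carer. These also need reconciling, because a GP assessment and a Plunket assessment need not cover the same things.

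**5. Other routes after 6 weeks**
- Monthly questions to 12 months ask about pertussis contact, contact with prolonged cough, and persistent cough in the infant.
- The 1-year contact covers pertussis and outstanding vaccinations.
- Footnote 3 of the schedule provides for the study team to measure an infant with no recorded values, but only for weight and head circumference.
- Unsolicited adverse events mentioned in the monthly contacts go into AE reporting. The SAE definition includes a congenital anomaly in the offspring and sets no age limit.

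So an abnormality first seen after 6 weeks can enter the data by two routes only: the developmental item, or an unsolicited report.

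**6. Scale.** The documents give neither the frequency of abnormalities nor the share recognised after 6 weeks, so the expected loss cannot be computed. With the target of 300, each infant missed lowers the proportion by 1/300 = 0.33 percentage points. For illustration, 3/300 = 1.0% would become 2/300 = 0.67%. The main protocol's own 95% interval for 1% of 300 (Study Two, Sample size and power) is 0.2–2.9%, so one infant is small beside sampling error. The error would still run in one direction.

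**The case against.** The strongest reply has four parts.

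*Congenital abnormalities are already covered.* The schedule places them at the 6-week check, and both the pregnancy-outcome page and the 6-week page have a field. No schedule row promises them at 3–6 months. This stands: the missing item contradicts no schedule row. It is a gap against a primary objective that sets no age limit, and a lesser matter than the missing examination fields, which do contradict the schedule.

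*Other data are collected after 6 weeks.* A reader might infer that infant findings after that visit go unrecorded. The documents do not support this. Growth, vaccinations, developmental concerns, monthly pertussis information and unsolicited adverse events are all recorded. The loss is confined to structured examination findings and structured capture of late-recognised abnormalities. Study One also covers hospital-coded anomalies in the first year of life, but as a separate de-identified linkage limited to hospital contact; it does not complete the Study Three description.

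*The Well Child book is not shown.* It may not record each organ system, so copied fields could stay blank and be read as normal. This is a fair warning and shapes the fix. The schedule itself, however, says that the examination is recorded there.

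*It may be late to change.* The Canterbury milestones place enrolment in July–December 2012 and the last 1-year data in December 2013. One main-protocol form carries a stamp of 29/10/2013. The main protocol nevertheless places the additional Canterbury data in 2014, and enrolment could be extended. The timing bears on cost and leaves the mismatch in place.

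**Conclusion.** The point holds in a limited form. The 3–6 month row promises a standardised clinical examination that its form cannot hold, and it cites the form for a different visit. The form also lacks a structured field for congenital abnormalities, so findings first recognised after the 6-week check depend on one developmental item or on unsolicited reports. This weakens the description of infant outcomes that Study Three names as a primary objective.

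A reader might go further and state how many infants are missed, or by how much the reported proportion is too low. Either figure would need an abnormality frequency, a share recognised late, and an assumption about what the unsolicited route picks up. The documents give none of these. The supportable statement is the direction (under-ascertainment) and the scale per infant shown above. The conclusion rests on the printed form being complete; its rows run without a break to the footnote.

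**What to change.** Amend the Canterbury Appendix 7:
- Add the examination block from the 6-week form (eye, heart, lung, neurological, hip or musculoskeletal) and the congenital-abnormality item with details, transcribed from the Well Child book.
- Give each item three answers: yes, no, not recorded. The third keeps a blank in the book from being counted as a normal finding and lets the report state how many infants were actually assessed on each item.

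In both copies of the schedule, change the 3–6 month citation from Appendix 6 to Appendix 7, and make the schedule and the form agree on whose assessment is accepted.

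The cost is a form amendment, with ethics notification if required, and a few more items to transcribe from a book already being consulted for weight and head circumference. Infants already past this visit may need their books re-abstracted. If that cannot be done for all of them, report the number with and without the added items.

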Appendix 1: Consent form

Appendix 2: Information sheet for mother

Appendix 3: Structured questionnaire for GP practice – information on mother

Appendix 4: Telephone survey questionnaire (adverse events in mother)

Appendix 5: Written questionnaire (medically attended adverse events in mother in first 4 weeks after vaccine)

Appendix 6: Structured questionnaire for GP practice (Details of pregnancy outcomes, standardised clinical examination of baby at 6-week check)

Appendix 7: Information from clinical examination by Plunket Nurse between 3-6 months of age (outcomes for infant)

Appendix 8: Monthly surveillance questions for mother and infant

Reporting

It will still be the responsibility of the physician administering the vaccine to report any adverse events using the local reporting system.

The study team will also report any adverse events to:

- o Local pharmacovigilance agency (CARM – Centre for Adverse Events Monitoring, University of Otago, website: carm.otago.ac.nz)

Adverse Event and Serious Adverse Event Definitions

An Adverse Event (AE) shall mean any untoward medical occurrence whether thought to have been caused by the vaccines or not and Serious Adverse Event (SAE) shall mean any adverse event which is fatal, life threatening, disabling or incapacitating, requires in-patient treatment or prolongs existing hospitalization, is a congenital anomaly in the off-spring of the patient or which may require intervention to prevent the previously stated outcomes.

If there is a report of an unsolicited event during phone calls with the mother regarding pertussis symptoms in the baby- this will follow the same reporting as above.

Budget

	NZD
Research Nurse 0.5 FTE for 1 year	35,000
Research Nurse 0.5 FTE for 1 year	35,000
Database and statistical support	15,000
Publication and Reporting	3000
Consumables	1500
Total	89,500

Study Milestones:

July 2012	First participants enrolled in study	
December 2012	Last participants enrolled in study (this potentially may be extended depending on enrollment)	
July 2013	Interim report due	
December 2013	Last of the 1 year follow up data will be collected	
March 2014	Final study report due	
May 2014	Submission of publication	

Ethics Approval

The GP claim forms for administration of Tdap includes a section for the woman to indicate if she is willing or not to be contacted by researchers.

This study has been approved by Upper South A Regional Ethics Committee – approval **URA/12/EXP/021**.

Study Title: Safety Monitoring of Adverse Reactions to Tdap Vaccine in Pregnancy

Participants are identified by their NHI (National Health Index) number to prevent duplications and ensure only one survey per participant is possible. The NHI numbers are removed prior to data analysis.

Data collected at the practice will include:

GP Name of Practice where woman is enrolled PHONE	
Name of woman who received vaccination Address	
Contact phone number of woman Email	
NHI number (this is not to provide identification but only used to ensure that there are no duplications of surveys)	
Date of Birth (of the woman)	
Ethnicity i.e. Maori/Pacific Island/NZ European/ Other.....	
Estimated due date (used to work out gestational age)	
Date of vaccine administration	

Arm which vaccine(s) were given in	
Vaccine product name and batch number	
Any immediate (within 30 minutes) side effects?	
Any other observations?	
Concomitant vaccines administered	
Previous pertussis booster given	
History of fever or vaccination reaction	
Health and underlying medical condition	
Inclusion Criteria:	
Received Tdap after 30 weeks gestation	Yes/No
Compliant with routine antenatal care, including at least 1 ultrasound early in pregnancy	Yes/No
Exclusion criteria:	
Receipt of Tdap (pertussis) vaccination before 30 weeks	Yes/No

Study Title: Safety Monitoring of Adverse Reactions to Tdap Vaccine in Pregnancy

The woman will be asked to provide data that will include the following for the period immediately following each dose of Tdap or influenza vaccine is received:

- Did she have any symptoms immediately after receiving the vaccination? (Yes/No)
later same day next day lasted-
- Was there any local reaction in the arm where the vaccination was given? (Yes/No)
or see below for details of classification
- Recall of fever (Yes/No) if yes what time frame did the fever – see below for details of classification
- Was the temperature measured? (Yes/No) if yes what was the measured temperature? – see below for details of classification
- Was there any other reactions
 - Nausea, vomiting or diarrhoea
 - Headache
 - Fatigue, lethargy or general weakness
 - Injection site reactions
 - Pain (including muscle or joint pain: not injection site pain)
 - Rigors/Shaking
 - Other (details)
- Was anti-fever medicine given (Yes/No) if yes was it given before or after vaccination?
- Did you need to call or see a doctor? (Yes/No) if yes who, where and why
- Had she received the Tdap vaccine previously? (Yes/No) if yes can she remember which brand it was?
- Can we contact them for more information (Yes/No)

All as per Brighton Collaboration where these definitions are available.^{2 3}

Definitions for local reactions and fever	
Local Reactions	Systemic Events

Level one diagnostic certainty is: Any description of morphological or physiological change at or near the injection site that is described or identified by a health care provider
 
Level two diagnostic certainty is: Any description of morphological or physiological change at or near the injection site that is described or identified by another person
	
Fever Endogenous elevation of at least one measured body temperature of $\geq 38^{\circ}\text{C}$
 
 • Time intervals 
 ○ 0 – 24hr Day 1 ○ 0 – 24hr Day 2 ○ Day 3-7... • Increments

Categories for event classification
 
 • Level 1: as specified in the case definition for a local reaction • Level 2: as specified in the case definition for local reaction 
Insufficient evidence for a local reaction
 
Not a case of a local reaction
 
Interval for onset of local reaction or first observation
 
 • >0-24 h • 25-48 h • 49-72h • 73h – 7 days • >7 days • Include numbers of subjects with local reactions newly present at each specified time as %. 
Diameter of the local reaction
 
 • >0.0 - <1.0 cm • ≥1.0 – 2.5 cm • ≥2.5 – 5.0 cm • ≥5.0 - <10.0 cm • ≥10.0 - <15.0 cm • ≥15.0 - <20.0cm • ≥20.0 - <30.0 cm • ≥30.0 cm 
Pain scale to include measure of functionality
 
 • 0 = No pain • 1 = Mild, still able to move arm normally • 2 = Moderate, hurts to move arm normally or to touch • 3 = Severe, unable to move arm 	
 ○ <38°C ○ 38.0-38.4°C ○ 38.5-38.9°C ○ Etc.... >41°C
--	--

Pertussis in Pregnancy Safety (PIPS) Study Protocol
Confidential
Not for Public Circulation or Reproduction

Appendix 5: Written questionnaire (medically attended adverse events in mother in first 4 weeks after vaccine)

Period _____ **to** _____

	Yes	No	Date started	Date Resolved	Resolving	Not Resolved	Resolved with lasting effects
Have you experienced any adverse events within the one month post vaccination?							
Any infections							
For example: urine infections, ear, nose, throat or lung infections, gastroenteritis, and skin infections. Circle which one.							
Muscle aches and pains							
New onset high blood pressure							
Severe nausea or vomiting							
Premature labour							
Premature rupture of membranes							
Severe abdominal pain							

Vaginal bleeding							
Depression or psychological disorders							
Unexplained itching of the skin							
Spontaneous abortion or threatened abortion							
2. Have you needed to see a doctor for the adverse event described above or for any other reason in the last month post-vaccination?							
 Emergency Room/After Hours  Hospitalisation  GP Practice							
2b. What was the diagnosis?							
2c. If there was no diagnosis, what were the signs and symptoms?							

2a. Can we contact the doctor for further details?
(If yes- provide Dr name and hospital/practice details)

Appendix 6.1 and 6.2: Structured questionnaire for GP practice (Details of pregnancy outcomes, standardised clinical examination of baby at 6-week check)

Study Title: Safety Monitoring of Adverse Reactions to Tdap Vaccine in Pregnancy

Pregnancy outcomes:	
Date of delivery	
Mode of delivery i.e. Vaginal Elective section Emergency section Forceps, or ventouse	
Name	
gender	
Complications related to birth Ie admitted to nicu (Provide details)	
Information about infant:	NHI – Apgars 1..... 510.....
Birth weight (gms)	
Length (cm)	
Head circumference (cm)	
Presence of congenital abnormalities	Yes/No

	If Yes, details.....
Gestational age at birth	Weeks _____

Study Title: Safety Monitoring of Adverse Reactions to Tdap Vaccine in Pregnancy

6 week check with GP	
Medically attended adverse events since birth	Yes  No  Hospitalisation  Emergency  GP Practice  Diagnosis:
weight	
Length (cm)	
Head circumference (cm)	
Presence of congenital abnormalities	Yes  No  If Yes, details.....
Details of 6-week check	Eye abnormalities Yes  No  Heart abnormalities Yes  No  Lung abnormalities Yes  No  Neurological abnormalities Yes  No  Hip or musculoskeletal abnormalities Yes  No 
Receipt of 6-week vaccination	Yes  No 

	Date:.....
Receipt of 3 month vaccination	Yes  No  Date:.....

Appendix 7: Information from clinical examination by Plunket Nurse between 3-6 months of age (outcomes for infant)

Study Title: Safety Monitoring of Adverse Reactions to Tdap Vaccine in Pregnancy

Information to be collected from Well Child book from any assessment from a Carer between the ages of **3 and 6 months**. i.e Plunket or GP

Date of assessment	
Age at assessment	
Weight in Kg	
Head circumference (cm)	
Length (cm)	
3 month vaccination (if missed on 6 week form)	Yes  No  Date:.....
5 month vaccination	Yes  No  Date:.....
Any concerns about developmental progress requiring medical referral	

* The Ministry of Health definition for age appropriate vaccination will be used, being receipt of the six-week immunisation within four weeks of due date and within six weeks of due date for the three-month, five-month and 15-month immunisations.

